4.5 PROTOCOL VIOLATIONS

Definition of protocol violations and deviations. Violation is an intended failure to adhere to the protocol such as wrong treatment being prescribed or administered or incorrect data being collected and documented. A protocol deviation is an unintended failure to adhere to the protocol and examples include errors in applying inclusion/exclusion criteria or missed follow-up visits due to error. Per protocol analysis is not planned for the study but deviations and violations will be monitored and reported throughout the study and detailed descriptively in the analysis report. If protocol deviation occurrences rise above 10% then sensitivity analysis as detailed in section 6.5 will be conducted. Some examples of protocol deviations which might occur in this study include;

- Patients not receiving randomised allocation
- Patients not receiving treatment within 7 days
- Ineligible participants being randomised

4.6 MISSING DATA

Primary and secondary count-based measures For the count-based measures two situations of missing are expected. Firstly, there will be those who have missing observations periodically through the study observation period but have remained in the study for these patients multiple imputation as described above will be adopted. The memory recall for the TLFB is 3 months therefore if a patient hasn't been to visits for a couple of months recall of up to 3 months is deemed reliable [4 - 6]. Where patients have gaps in their recall on the primary outcome (at most this would be 3 months) we would use the available data to impute for the patient. Sensitivity analysis will be conducted on this imputation using a best-case worst-case analysis, see section 6.9 for more details.

Secondly, there will be some cases of participants who completely drop out of the study during the observation period i.e. withdrawals or loss to follow ups. For these patients on the primary outcome and secondary count-based measures an offset (censoring) will be used to represent different exposures rather than multiple imputation.

Furthermore, some of the primary and secondary end points (TLFB) are based on self-report and UDS tests. Where data is available for self-report and UDS, if the results are inconsistent the UDS data will override the self-report, as indicated in section 5.2. Essentially where UDS is not available this does not result directly in missing data for the outcome as the self-report

will provide this data. However, the reliability of the self-report may be impacted therefore sensitivity analysis on missing UDS data will be conducted, see section 6.9 for more detail.

Continuous outcome measures

Missing observations are expected within the dataset. For missing items within an outcome measure, the published rules for completing missing data for the relevant measure will be applied. Where there are no missing data rules for the measure, if the number of missing items on an outcome is 20% or less, then the missing value for the item will be substituted by the individual's mean score for the remaining items on the scale (Bono, Ried, Kimberlin and Vogel 2007). If there are more than 20% missing items in the scale the outcome measure will not be calculated for the participant at that time point and multiple imputation methods will be used.

Predictive mean matching multiple imputation methods will be adopted for an outcome measure total score if missing data arises above 5%. For multiple imputations, the number of imputations completed will be dependent upon the percentage of missing data [2]. The missing outcome measures will be imputed using group allocation and stratification variables along with any baseline characteristics that are deemed to be predictors of missingness. Baseline characteristics will be assessed for being predictors of missingness by running statistical tests on completers versus non completers and evaluating if any differences are present between the two.

Baseline factors to be assessed as predictors of missingness include;

- Centre
- Current injecting status
- Length of current treatment episode
- Preference of MET or BUP-SL
- Use of cocaine in the past month
- Sex at birth
- Age
- *Ethnicity
- Baseline outcome scores on the following measures:
 - QIDS-SR
 - WSAS
 - PRO-S

- ALC-QFM
- ADAPT (all subscales)

*Ethnicity is being collected with five categories - Black, White, Mixed, Asian and other. Depending on the prevalence of responses in each of these categories, the variable will be treated either with all 5 categories as collected or if appropriate will be dichotomised into 'White' and 'Non-White' if the range across categories are low.

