7 onwards	168 onwards	Week 24 onwards (every 28 days)	Up to 42 days since previous dose	100mg or 300mg

If the participant misses a scheduled maintenance of XR-Bup no adjustment in dose is required, if they receive this dose within 60 days of their last injection. If the participant does not receive an XR-Bup dose within 60 days of their last injection, the participant is not withdrawn from study treatment; but a clinical assessment by the principal investigator (PI) is needed to determine if there has been any illicit opioid use and the optimal starting dose.

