- **Measure 1;** Total retention time - Days enrolled in maintenance medication for opioid use disorder (OUD) from first day following grace period (day 8) to day 168 (across 161 days weeks 2 to 24)
- **Measure 2;** Survival time - Days from randomisation to first discontinuation (i.e. time (days) enrolled in study treatment).
- ***Measure 3;** Time (days) enrolled in study treatment (retention) from week 24 to date last participant randomised plus 9 months.

*Measure 3 Will be analysed as part of the extended phase of the study and detailed in a separate SAP

Objective 4 OUD and CUD remission status

- Assessed by Standard Clinical interview for Dependence - research version (SCID-RV)
 - Remission status (Yes/No) at 12 weeks
 - Remission status (Yes/No) at 24 weeks

Objective 5 Clinician rated impression of patient response to treatment (at 24 weeks)

- **Measure 1;** Clinical Global Impression scale (severity and improvement - CQI-S/CGI-I)
- **Measure 2;** Addiction Dimensions for Assessment and Personalised Treatment (ADAPT)

Objective 6 Patient reported recovery outcomes (at 24 weeks)

Measure 1; Craving response using Craving experience questionnaire (CEQ-F)

Measure 2; Visual analogue craving rating (Need) (VAS-N)

Measure 3; Visual analogue craving rating (Want) (VAS-W)

Measure 4; Social functioning using Work and Social Adjustment Scale (WSAS)

Measure 5; Depression using Quick inventory of Depressive Symptomatology (QIDS-SR)

Measure 6; Improvement and Recovery using Substance Use Recovery Elevator (SURE)

Measure 7; Patient Reported Outcome Status (severity and improvement - PRO-S/PRO-I)

Measure 8; Emotion regulation using Difficulties in Emotion Regulation Scale short form (DERS-SF)

Measure 9; Alcohol quantity, frequency, maximum consumption (ALC-QFM (TOP) - quantity and frequency only - maximum will be reported descriptively).

Objective 7 Mediation analysis

Mediation of craving, work and social adjustment, and cognitive function on outcome.

Mediator measures;

- Visual analogue scale (VAS) for the perceived need and want for non-medical opioids and cocaine (VAS-N and VAS-W)
- Craving Experience questionnaire, frequency version (Heroin) (CEQ-F-H)
- Quick Inventory of Depressive Symptomatology – Self-Report (QIDS-SR)
- Montreal Cognitive Assessment (MoCA)
- Work and Social Adjustment Scale (WSAS)

Moderator measures;

- Sex at birth

- Age
- Current injecting status
- Centre
- Measure/Outcome baseline

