APPENDIX 2 – OBJECTIVES AND ASSOCIATED OUTCOME MEASURES AND CHARACTERISTICS

Objective	Outcome Measure	Time Period	End point	Variable Type	Analysis Model	Scoring
One - effectiveness of BUP-XR and MET/BUP-SL	Primary outcome					
	Number of days abstinent from heroin	Days 8 – 168	24 weeks	Count	Poisson Regression	Count of days abstinent
	Secondary outcomes					
	Number of days abstinent from cocaine	Days 8 – 168	24 weeks	Count	Poisson Regression	Count of days abstinent
	Number of days abstinent from Benzodiazepines	Days 8 – 168	24 weeks	Count	Poisson Regression	Count of days abstinent
	Longest time in days continuously abstinent from heroin	Days 8 – 168	24 weeks	Count	Poisson Regression	Max Count of days consecutively abstinent
	Longest time in days continuously abstinent from cocaine	Days 8 – 168	24 weeks	Count	Poisson Regression	Max Count of days consecutively abstinent
	Longest time in days continuously abstinent from Benzodiazepines	Days 8 – 168	24 weeks	Count	Poisson Regression	Max Count of days consecutively abstinent
Two – Safety profile	Number of safety events	Study enrolment to 24 weeks	24 weeks	Count	Descriptive	n/a
Three – Treatment retention	Total retention time	Days 8 – 168	24 weeks	Count	Poisson Regression	Count of Days enrolled in maintenance medication for OUD
	Survival time to study withdrawal	Randomisation date to first discontinuation	24 weeks	Time to event	Cox regression	Time to first discontinuation
Four – OUD and CUD remission status	SCID-RV interview	Baseline to week 24	12 weeks & 24 weeks	binary	(Binary) logistic regression	Remission status (Yes/No) indicated by SCID-RV (see appendix 3 for SCID scoring)

Objective	Outcome Measure	Time Period	End point	Variable Type	Analysis Model	Scoring
Five – Clinician rated impression of patient response to treatment	Clinical Global Impression scale (severity and improvement - CQI-S/CGI-I)	Baseline to week 24	24 weeks	Ordinal	Ordinal logistic Regression	See Appendix 3
	Addiction Dimensions for Assessment and Personalised Treatment (ADAPT)	Baseline to week 24	24 weeks	Continuous	GLM	See Appendix 3
Six – Patient reported recovery outcomes	Craving response using Craving experience questionnaire (CEQ-F)	Baseline to week 24	24 weeks	Continuous	GLM	See Appendix 3
	Visual analogue craving rating (Need) (VAS-N)	Baseline to week 24	24 weeks	Continuous	GLM	See Appendix 3
	Visual analogue craving rating (Want) (VAS-W)	Baseline to week 24	24 weeks	Continuous	GLM	See Appendix 3

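### The SAP's exposure offset for study dropouts also covers total retention time, where it dilutes the arm difference, and the longest abstinent run, where it biases modestly against the better-retained arm

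*SAP*

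**What the plan says.** SAP 4.6 separates intermittent gaps, which are imputed, from "participants who completely drop out of the study during the observation period i.e. withdrawals or loss to follow ups". For the second group the rule, in place of multiple imputation, is: "For these patients on the primary outcome and secondary count-based measures an offset (censoring) will be used to represent different exposures". The exposure variable is not defined, and no secondary count is exempted.

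Appendix 2 gives variable type Count and model Poisson regression for two kinds of outcome besides the days-abstinent counts:

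- Total retention time, scored as "Count of Days enrolled in maintenance medication for OUD". SAP 5.2 (Objective 3, Measure 1) defines it as "Days enrolled in maintenance medication for opioid use disorder (OUD) from first day following grace period (day 8) to day 168", a window of 161 days.
- Three longest-run outcomes, of which the first is "Longest time in days continuously abstinent from heroin"; the others are for cocaine and benzodiazepines.

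SAP 6.7 repeats the Poisson model for count variables. Objective 3 also has a Measure 2, defined in 5.2 as "Days from randomisation to first discontinuation (i.e. time (days) enrolled in study treatment" and analysed by Cox regression. The offset rule does not reach it.

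**The concern.** An offset turns a count into a rate per day observed. That suits an outcome that accumulates in proportion to observation time, such as abstinent days. It does not suit the other two kinds.

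Total retention time measures how long people stay. If a person leaves treatment and study together, the numerator and the exposure are the same number, and the early exit vanishes from the estimate. A longest run is a maximum, which flattens as observation lengthens. Dividing it by days observed therefore credits short follow-up.

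Treatment retention is a stated secondary objective. One of its two phase 1 measures would be pulled towards no difference, and the longest-run outcomes would be tilted towards the arm that loses more people. The planned sensitivity analyses would not reveal this. In SAP 6.9 the best-case/worst-case check on missing self-report covers only the primary outcome, and the check on missing urine screens does not address days after dropout.

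**Working it through.** **The plan's own figures.** The documents give no figure for the offset. The nearest is the 15% attrition allowance in SAP 4.1, which enters as N = (1.960 + 1.282)² × (2 + 2/1.23) / (0.6 × 5.75 × (ln 1.23)²) = 258, then 258/0.85 = 304, the stated total. The exposure of 5.75 is 161/28, inferred from the monthly rate and the 28-day reference period.

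**Individuals, retention.**

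- Leaves treatment and study on day 40: days 8 to 40 are 33 days, so 33/33 = 1.00.
- Completes: 161/161 = 1.00.
- Completes with a gap, 120 days on medication: 120/161 = 0.75.
- Stops medication after 60 days of the window but is followed to day 168: 60/161 = 0.37.

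The early exit disappears only when leaving treatment coincides with leaving the study.

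**Arms, retention.** From the documents: a 161-day window and a Poisson model with an offset. Assumed: proportion p still retained at day 168 of 80% v 60%, a constant leaving rate, and a share f of treatment leavers who leave the study the same day, the rest being followed to day 168. With only arm in the model, the fitted rate is total days retained over total days observed.

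- Mean days retained: m = 161(1 − p)/(−ln p). For 80%: 161 × 0.2/0.2231 = 144.3. For 60%: 161 × 0.4/0.5108 = 126.1. Ratio 1.14.
- Mean days among leavers: e = (m − 161p)/(1 − p). For 80%: 77.5. For 60%: 73.7.
- Mean days observed: x = 161 − f(1 − p)(161 − e).

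| f | x, 80% arm | x, 60% arm | m/x, 80% arm | m/x, 60% arm | Ratio with offset |
|---|---|---|---|---|---|
| 0 | 161.0 | 161.0 | 0.896 | 0.783 | 1.14 |
| 0.50 | 152.7 | 143.5 | 0.945 | 0.878 | 1.08 |
| 0.75 | 148.5 | 134.8 | 0.972 | 0.935 | 1.04 |
| 1.00 | 144.3 | 126.1 | 1.000 | 1.000 | 1.00 |

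Other assumptions show the same pattern. With 70% v 50%, 1.17 falls to 1.09, 1.05 and 1.00 at f = 0.50, 0.75 and 1.00. With 80% v 50% and uniform exit days (152 per arm, 300 simulated trials), 1.20 falls to 1.16, 1.11, 1.06 and 1.00 at f = 0.25, 0.50, 0.75 and 1.00.

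**Longest run.** Simulated with the same behaviour in both arms: 60% abstinent days, assumed day-to-day correlation 0.8. The true ratio is 1.00. The mean longest run per observed day is 0.55 at 14 days, 0.36 at 56 and 0.20 at 161. With study exit following the 80% v 60% pattern above:

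- Without the offset, the better-retained arm has more time to build a long run: ratio about 1.09.
- With the offset, that ratio is divided by the ratio of days observed: 1.09/1.14 = about 0.95.

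With 90% v 80% the two ratios are 1.04 and 0.98. With 80% v 50%, uniform exit and 0.9 day-to-day persistence they are 1.11 and 0.92. In each case dropping the offset reverses the direction of the bias and makes it larger.

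**The case against.** Several points limit the concern, and they stand.

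- The offset is triggered by leaving the study, while retention counts days on medication. Protocol 8.5 asks people who withdraw whether they will still provide data and seeks at least the follow-back interview and urine screen. If 15% attrition means study loss, then against the assumed average of (20% + 40%)/2 = 30% leaving treatment it is half of leavers, which is the mildest diluted row (1.08).
- Measure 2 matches the wording of the protocol's retention endpoint (Protocol 10.2, item 3) and carries no offset, so the objective is still answered.
- SAP 4.3 treats all secondary outcomes as exploratory, and the longest run is not among the 19 secondary parameters in Protocol 10.2.

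None of this exempts Measure 1 or the longest runs. Moreover, the two exits do coincide by rule on one route: Protocol 8.3 withdraws from the trial those allocated to the injection who do not go on to receive it.

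A reader might also infer more than the documents support:

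- *That all count outcomes are spoiled, including the primary.* For days abstinent, a rate per observed day is a coherent model if dropout is non-informative.
- *That early leavers distort the comparison almost threefold.* The ratio 0.55/0.20 = 2.75 compares individuals. The arm estimate is total count over total exposure, so a person seen for 14 days carries little weight, and the distortion there is about 5%.
- *That the Cox measure is unusable because, after a long injection gap, "the participant is not withdrawn from study treatment".* That sentence in Protocol 6.3 belongs to a missed-injection rule that calls for a clinical assessment. The Appendix 2 time period and scoring for Measure 2 both agree with 5.2. Only the row title, which speaks of study withdrawal, is out of line.

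**Conclusion.** The point holds for total retention time and, more modestly, for the longest-run outcomes. As written, SAP 4.6 dilutes the Measure 1 retention ratio from 1.14 to between 1.08 and 1.00 when 50% to 100% of treatment leavers also leave the study. It gives a longest-run ratio of about 0.95 where the truth is 1.00. Complete cancellation of the retention effect is the extreme case and requires every treatment leaver to leave the study at the same time.

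The Cox retention measure and the days-abstinent counts are not affected by this error. The correction should be made before database lock, but the primary conclusion does not depend on it. The sizes rest on assumed retention, exit timing, overlap between treatment and study exit, and clustering of abstinent days; the documents give no dropout pattern.

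**What to change.** In SAP 4.6 and Appendix 2:

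1. Limit the offset to the days-abstinent counts. Define its exposure variable, including what happens to a participant with no observed day from day 8 onward, for whom a log offset is undefined.
2. Analyse total retention time as days on medication out of a fixed 161, without an offset. Where study follow-up ended, take the days from the BUP-XR Injection Log and the BUP-SL/MET Medication Record, and state a rule for days that neither source covers.
3. For the longest run, do not simply remove the offset. State a rule for post-dropout days, for example imputing them or treating the run as censored at dropout, give the assumption behind it, and report the result as exploratory. An analysis of full-follow-up participants alone selects on a post-randomisation event and does not solve the problem.
4. Align the Appendix 2 row title for the Cox measure with the definition in 5.2, first discontinuation.

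The cost is SAP wording and modest programming. SAP 4.4 already plans to use both medication records for adherence, so no new collection should be needed where they continue after study exit.

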4.7 ASSUMPTION CHECKING

All assumptions relating to the models will be checked and evaluated whether appropriate to use with the data. If any of the assumptions are substantially violated then appropriate non-parametric tests will be conducted. Appendix 4 contains details of the assumptions associated with each model and the methods to be used to assess these assumptions.

Outliers or unusual values will be assessed by running Grubbs [7] test for outliers and visually inspecting a boxplot. No outliers will be discarded if they are within plausible range. Primary analysis will be conducted keeping the outliers in the dataset and if necessary, sensitivity analysis will be conducted by removing the outliers and evaluating any effects on the results and conclusions of analysis. Any outliers removed will be fully reported.

The distribution of the data will be checked. For the count data a decision will need to be made as to which analysis method to use for the outcome based on the distribution of the data. Appendix 1 contains a flow diagram to be followed to decide which analysis model is to be run based on the data distribution.

For continuous data a decision will be made as to whether a transformation should be applied to the data and if so which transformation should be used. If transformation is required the distribution of the transformed data will be checked. Analysis will be reported on the original scale, transforming variables back. If a transformation is inappropriate then non parametric analysis methods will be considered.

For the logistic regressions, if detection rates (number of responses observed) are very low, where appropriate, either a Firth's Bias-Reduced Logistic Regression will be conducted or descriptive statistics reported.

5. DATA

KCTU MACRO database;

All baseline and follow-up data will be entered on the online InferMed MACRO electronic data capture (EDC) system (infermed.com). This system is regulatory compliant (GCP, and the EC Clinical Trial Directive). An electronic case report form (eCRF) using the MACRO EDC will be programmed by the KCTU and hosted on a dedicated secure server. The eCRF system will have full audit trail, data discrepancy functionality, database lock functionality, and supports real time data cleaning and reporting. The Trial Manager will request usernames and passwords to any new researchers. Only those authorised by the Trial Manager will be able to use the system.

After written recording, each research worker will aim to transcribe data onto the eCRF within one working week of a participant assessment. After completion of all follow-ups and prompt entry of data, the Clinical Research Associate (CRA) will review the data and resolve queries with sites. At the end of the trial, each centre will be supplied with their eCRF data for storage. This will be filed locally for any future regulatory or internal audit.

Database lock for phase I will be undertaken within approximately 3 months of last patient, last visit and will be controlled by TMG of participants enrolled in groups 1 and 2. Database lock for phase II will be within approximately 3 months of last patient, last visit and will be controlled by TMG of participants enrolled in groups 3 and 4. This will be once the data has been monitored, all queries resolved and PI sign off has been obtained for participants in the BUP-XR and BUP-SL/MET (including BUP-SL-NX and ESP) arms.

KCTU Randomisation System;

The King's Clinical Trials Unit Randomisation system will be used in EXPO. This will be a secure password-protected, web-accessed system.

Once a patient has consented and it is confirmed that all potential medication is in place within the next 7 days, all baseline data collected and eligibility confirmed, the staff member will log

into the randomisation system (www.ctu.co.uk) and randomise the participant, detailing the relevant stratification factor information;

- *(a) Site (South London, the West Midlands, Greater Manchester, Newcastle and Tayside)
- (b) Current (last 28 days) drug injecting status (yes/no)

*Note there are four systems built for the study three for South London and one for the other sites.

1 system for other sites at 1:1 ratio XR BUP-SL and MET/BUP-SL

1 system South London at ratio 4:4:1:1 BUP-XR, MET/BUP-SL, BUP-XR + PSI, MET/BUP-SL + PSI

1 system South London at ratio 1:1:1:1 BUP-XR MET/BUP-SL, BUP-XR + PSI, MET/BUP-SL + PSI

1 system South London at ratio 1:1: BUP-XR + PSI, MET/BUP-SL + PSI

The randomisation procedure will use stratified random blocks of varying size to ensure even allocation. See section 4.2 for more details on randomisation.

